(DMGS). 77% of patients with diabetic nephropathy on 10 year biopsy did not have diabetes pre-transplantation, and 46% were in patients without overt diabetes pre- or post-transplantation, but with characteristics of prediabetes including fasting hyperglycemia and obesity. Furthermore, kidney transplants with DMGS had greatly inferior graft survival (Figure 1). These data suggest that a paradigm shift is needed to improve the long-term graft survival for kidney transplants.

PTDM is a pervasive problem. In a review of UTHSA kidney transplant recipients, the incidence of PTDM was 43% among Hispanics and 33% in non-Hispanic whites. Patients with PTDM had a higher BMI (BMI=30.4 kg/m²) compared with patients without PTDM (BMI=27.7 kg/m²). Based on preliminary data from our collaborative analysis of the University of Michigan Transplant Center cohort, 15% of 345 kidney transplant recipients who did not have diabetes pre-transplant had developed PTDM based on an OGTT done at 6 months post-transplant, and another 24% were prediabetic based on 2-hour glucose values which met the criteria for IGT. Similarly, the Mayo experience (a predominantly Caucasian population) noted a 33% incidence of IFG at 1 year among kidney transplant recipients without diabetes pre-transplant.

Study endpoints

Primary Efficacy Endpoint:

Incidence of diabetes at 24 months after kidney transplantation.

Diabetes is defined based on ADA criteria for diagnosis of diabetes;

HbA1C>6.5%

or FPG>126 mg/dl (fasting is defined as no caloric intake for at least 8 hours)

or 2h plasma glucose >200 mg/dl during an OGTT

or random plasma glucose >200 mg/dl in patient with classic symptoms of hyperglycemia

Based on published data, we expect that 30% of untreated patients with prediabetes at 4 months will develop diabetes by 12 months after transplantation. See statistical assessment section.

Patients also will be followed up to 20 months after enrollment for progression to other endpoints

Secondary endpoints

- To evaluate the prevention of progression to diabetes by 24 months after transplantation
- To evaluate the safety and tolerability of Exenatide SR
- To compare hemoglobin A1c levels in patients treated with Exenatide SR + SOC vs. SOC alone at 24 months after kidney transplantation.
- To compare the incidence of mesangial expansion >20% in patients treated with Exenatide SR + SOC vs. SOC alone at 24 months after kidney transplantation.

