Safety will be assessed using incidence of all adverse events (AEs), serious adverse events (SAEs), treatment-emergent adverse events (TEAEs) and AEs leading to study withdrawal; review of laboratory data, including hematology, renal function, biochemistry and microbiology and malignancies; new concomitant medication usage; hospitalization rates; and vital signs. Adverse events will be classified for serious adverse events using standard regulatory criteria.

Statistical analysis plan.

Study design and analysis will be performed according to intention to treat principles. Time to development of PTDM will be compared utilizing Kaplan-Meier curves generated according to the product limit method utilizing log-rank tests to evaluate intergroup differences. Risk adjustment for baseline differences between groups will be assessed according to multivariate proportional hazards models. Data on patients who withdraw or are lost to follow-up will be censored at the time of last visit. Comparisons of repeated measures between groups including the secondary endpoints outlined above will be performed utilizing general linear mixed models with transformation of data to logarithm forms when appropriate. These comparisons will be made with inclusion of subjects who withdraw within the follow-up period. Sensitivity analysis excluding these patients will also be performed.

Needed sample size was calculated according to development of PTDM based on utilization of a 2-sided chi-squared test at a 5% significance level and 80% power. The incidence of PTDM reported after kidney transplant varies from 2-50% with best estimates indicating that approximately 30% of patients will develop PTDM.^{3,4,41,42} The SCALE trial comparing GLP-1 receptor agonists to placebo showed an 80% reduction in development of type 2 diabetes.²¹ Other clinical trials evaluating prevention of diabetes showed a 30% risk reduction with metformin and 55-72% reduction with TZDs.^{29,43} Thus, sample size was calculated based on a proportion of 30% incidence of PTDM in the control group and 80% risk reduction in the experimental group (consistent with SCALE trial). A total of 81 (54:27 according to 2:1 randomization) patients will be required to achieve the power and significance levels above. In our preliminary data, 24-33% of kidney transplant recipients meet prediabetes criteria. We would expect that full enrollment would take 24 months.

Data management plan

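### Does the 30% control rate behind the 81 patients need to be re-derived because its two descriptions differ and neither is a month-24 rate for the enrolled patients?

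*Combined protocol and SAP*

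**What the plan says.** The sample-size paragraph of the Statistical analysis plan specifies a two-sided chi-squared test at 5% with 80% power. It notes that reported PTDM incidence ranges from 2% to 50%, with "best estimates indicating that approximately 30% of patients will develop PTDM". It then states: "Thus, sample size was calculated based on a proportion of 30% incidence of PTDM in the control group". An 80% risk reduction is taken from a cited GLP-1 receptor agonist prevention trial, and the result is: "A total of 81 (54:27 according to 2:1 randomization) patients will be required to achieve the power and significance levels above". On recruitment, it says that "24-33% of kidney transplant recipients meet prediabetes criteria".

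The Primary Efficacy Endpoint section sets the endpoint at month 24 after transplant but adds that "we expect that 30% of untreated patients with prediabetes at 4 months will develop diabetes by 12 months after transplantation", followed by "See statistical assessment section". The statistical section has a 30% control rate but no month-4-to-month-12 derivation of it.

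Three other places bear on this:

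- **Background** dates a 30% PTDM rate to the first two years after transplant. It shares one citation with the sample-size paragraph.
- **Study design/schedule** plans about half the entries at month 4 and half at month 12, with 20 or 12 months of follow-up. Exclusion criteria remove patients who are already diabetic.
- **PRELIMINARY DATA** reports, for one centre, "15% of 345 kidney transplant recipients who did not have diabetes pre-transplant had developed PTDM based on an OGTT done at 6 months post-transplant", with another 24% prediabetic. For a different centre it reports PTDM of 43% in Hispanic and 33% in non-Hispanic white recipients, with no time horizon.

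**The concern.** The same figure is attached to two different populations and time windows, and neither is the trial's own. A rate in all recipients, counted from transplant, includes people who become diabetic before entry, and the trial excludes them. A rate from month 4 to month 12 stops a year before the endpoint. It cannot describe the month-12 entrants either, because anyone it counts is ineligible for that half.

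The stake is power. At 30% versus 6% the trial expects only 27 × 0.30 + 54 × 0.06 = 8.1 + 3.2 = 11.3 events, so the required number is sensitive to this one input. If the true control rate were well below 30%, 81 patients would be too few. If it were well above, fewer would do.

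**Working it through.** **1. Reproduce the 81.** Inputs from the Statistical analysis plan: p1 = 0.30; p2 = 0.30 × (1 − 0.80) = 0.06; allocation 2:1; two-sided 5%; 80% power. Pooled-variance formula for the control arm, with p̄ = (0.30 + 2 × 0.06)/3 = 0.14:

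n = [1.960 × √(1.5 × 0.14 × 0.86) + 0.842 × √(0.30 × 0.70 + 0.06 × 0.94/2)]² / 0.24² = 26.85

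This rounds up to 27 control and 54 exenatide, total 81, as stated. Power at 27:54 is 80.2% by the formula and 82.4% by exact enumeration of the chi-squared test.

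**2. Vary the control rate**, keeping the 80% reduction, the 2:1 ratio and the test:

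| Control rate | Total for 80% power | Exact chi-squared power at 81 |
|---|---|---|
| 20% | 132 | 63% |
| 25% | 102 | 74% |
| 30% | 81 | 82% |
| 35% | 69 | 89% |
| 40% | 57 | 93% |

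The planned primary comparison is a log-rank test. It was simulated with half the patients followed for 20 months and half for 12, a constant hazard and no loss. For assumed month-4/month-12 control rates of 30/10, 30/20, 40/20 and 50/30, power is about 64%, 75%, 83% and 94%.

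**3. Do the documents say which way the 30% errs?** Carry each description forward at a constant hazard (an assumption, for illustration).

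- *Month-4 prediabetes, 30% in 8 months.* Over 20 months: 1 − 0.70^(20/8) = 59.0%. Over 12 months: 1 − 0.70^(12/8) = 41.4%. The 50:50 mean is 50.2%, for which 42 patients would do.
- *All recipients, 30% in 24 months.* Over 20 months: 1 − 0.70^(20/24) = 25.7%. Over 12 months: 1 − 0.70^(12/24) = 16.3%. The mean is 21.0%, which needs 126 patients. Selecting for prediabetes would raise this rate by an amount the documents do not give.

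The planned 30% lies between the two.

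**4. Can the preliminary data settle it?** Subtract the 15% diabetic at month 6 from a cumulative rate, per 100 recipients (24 prediabetic, 61 with normal glucose). If prediabetics progress at 30%, they supply 0.30 × 24 = 7.2 cases.

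- *Cumulative 30%.* Later cases 15, or 15/85 = 18% of non-diabetics. The rest progress at 7.8/61 = 12.8%, so prediabetics need a risk ratio of about 2.3.
- *Cumulative 33%.* Later cases 18, or 18/85 = 21%. The rest progress at 10.8/61 = 17.7%, a ratio of about 1.7.
- *Cumulative 43%.* Later cases 28, or 28/85 = 33%. No excess risk in prediabetics is needed.

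The answer depends on which cohort is chosen, and each line subtracts one cohort from another. The month-6 rate is OGTT-based, whereas the trial uses OGTT only when clinically indicated. Month 6 is also the late edge of the month-4 entry window (days 90–180).

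**5. Would a record review fix the number?** At about 600 transplants a year and 24–33% prediabetic, two years give at most 2 × 600 × 0.24 = 288 to 2 × 600 × 0.33 = 396 patients, before pre-transplant diabetes is removed. The 95% half-width at 30% is 1.96 × √(0.21/n): 5.3 points at 288 and 4.5 at 396. For each entry group separately (144 to 198 patients) it is 7.5 to 6.4 points. The alternatives of 102, 81 and 69 patients lie 5 points apart.

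**6. The follow-up sentence.** "Patients also will be followed up to 20 months after enrollment for progression to other endpoints" does not conflict with the 20 or 12 months in Study design/schedule; 20 is the maximum of the two.

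**The case for a change.** The strongest case for a change is that a sample size should rest on a rate for the patients and the time point being studied. A reader who follows the cross-reference from the endpoint section finds a different population and no horizon. The plan nowhere argues that prediabetes offsets the removal of early cases. If the endpoint-section figure is right and first occurrences are counted, month-4 entrants are already at 30% by month 12, so a 30% mean requires month-12 entrants at or below 30%. With about 11 expected events, a 5-point error moves the total to 102 or 69.

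The textual part of this stands: the endpoint-section sentence does not fit a month-24 endpoint, and the 30% is not argued for the enrolled patients. The rest is weaker. The 30% floor for month-4 entrants holds only if a patient once diabetic stays counted; the Study objectives separate diabetes at month 24 (primary) from progression by month 24 (secondary). The sample-size paragraph alone supplies the input to the 81, and the endpoint section only refers to it. The shift to 102 or 69 is conditional on a rate that nobody has, and the records proposed to supply one are too imprecise to establish it.

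**Conclusion.** No change is called for. The 81 is correct for its stated inputs, the 30% lies within what the documents' own figures allow (roughly 21% to 50% under a constant hazard), and the direction of any error is unknown. No stated number or power is shown to be wrong.

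A wrong control rate would cost or add power: about 63% at a true 20% and 93% at a true 40%, if the 80% reduction holds. It would not bias the treatment comparison, raise the type I error or alter how the data are analysed. The plan also discloses the 2–50% range behind its choice and describes itself as a feasibility trial, so an approximate planning rate is a fair trade-off.

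What remains is a loosely worded expectation in the Primary Efficacy Endpoint section. A statistician would read past it by taking 30% as the assumed month-24 control rate averaged over the two entry times. Resetting the enrolment target from a record review would bring no demonstrable gain, because its margin of error is as wide as the gap between the candidate totals.

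These conclusions assume the 80% reduction and 2:1 allocation throughout, and a constant hazard where rates are carried forward. The cohort subtractions only show that the preliminary data cannot settle the rate.

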We identified 17 kidney transplant recipients who were started on GLP-1 agonists for diabetes in our institution. Discontinuation rate was 17% (similar to non transplant population). Medication was effective in reducing weight, controlling diabetes and decreasing the insulin requirements. Abstract submitted to American Transplant Congress (attached).

Collecting, monitoring and reporting of serious adverse events.

Adverse events will be recorded by PI/co-PI or the care team member in patient medical record using a recognized medical term or diagnosis that accurately reflects the event. Patients will be encouraged to contact care team members by the phone or electronically and reported events will be reviewed by PI/co-PI. Patients will have labs monitored and visits scheduled per standard of care as outlined in the protocol. Additionally, PI/co-PI or designated person on research team will follow up with patient by the phone call or electronically at 7-14 days and 90± 7 days after initiation of drug with open ended questions. Adverse events will be considered based on patient reported symptoms, examinations and laboratory data. Adverse events will be assessed by the investigator for severity, relationship to the investigational product, possible etiologies, and whether the event meets criteria of an SAE and therefore requires immediate notification to AstraZeneca Patient Safety.

Study recording period and follow-up for adverse events and serious adverse events

Adverse events and serious adverse events will be recorded from time of signature of informed consent, throughout the treatment period and including the follow-up period.

All SAEs will be reported, whether or not considered causally related to the investigational product, or to the study procedure(s). The reporting period for SAEs is the period immediately following the time that written informed consent is obtained through 90 days after the last dose of investigational product. The investigators are responsible for informing the Ethics Committee and/or the Regulatory Authority of the SAE as per local requirements.

The investigator will inform the FDA, via a MedWatch form, of any serious or unexpected adverse events that occur in accordance with the reporting obligations of 21 CFR 312.32, and will concurrently forward all such reports to AstraZeneca. A copy of the MedWatch report will be emailed to AstraZeneca (TCS vendor) at the time the event is reported to the FDA.

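### The 81 patients are the number with a 24-month result that gives 80% power, but 81 is also the enrolment total, with no allowance for withdrawal or loss

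*Combined protocol and SAP*

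**What the plan says.** All the inputs stand in the Statistical analysis plan section. The trial was sized on "utilization of a 2-sided chi-squared test at a 5% significance level and 80% power", assuming "a proportion of 30% incidence of PTDM in the control group and 80% risk reduction in the experimental group". The result is: "A total of 81 (54:27 according to 2:1 randomization) patients will be required to achieve the power and significance levels above". The next sentences turn to how long enrolment will take, and no other enrolment total is given anywhere.

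The effect size is borrowed: "The SCALE trial comparing GLP-1 receptor agonists to placebo showed an 80% reduction in development of type 2 diabetes". The documents do not say whether that reduction is an intention-to-treat or an on-treatment estimate.

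On analysis, the section says "Study design and analysis will be performed according to intention to treat principles". It compares time to diabetes by Kaplan-Meier curves and log-rank tests, and adds: "Data on patients who withdraw or are lost to follow-up will be censored at the time of last visit". No loss rate is given.

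On stopping treatment, the Preliminary data section that follows Study Coordination reports: "We identified 17 kidney transplant recipients who were started on GLP-1 agonists for diabetes in our institution". It continues: "Discontinuation rate was 17% (similar to non transplant population". For patients who stop the drug, the only follow-up specifically described is a 30-day safety period (end of the Stopping Rules section) and a contact within 30 days after stopping for adverse events (Study design/schedule). The endpoint falls 12 or 20 months after enrolment.

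**The concern.** A sample size that meets its power target only when every patient contributes a 24-month result should be inflated, or its power restated, if the plan expects some patients not to contribute. Here the plan expects withdrawal and loss, and its own experience includes patients stopping this drug class, but neither enters the calculation.

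The 80% is the only numerical justification for the trial's size. If it is optimistic, a non-significant result would be read as stronger evidence against exenatide than 81 enrolled patients can supply.

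**Working it through.** **Inputs from the plan.** Control risk pC = 30%. Exenatide risk pE = 30% × (1 − 0.80) = 6%. Two-sided 5% test (z = 1.960), 80% power (z = 0.842), allocation 2:1.

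**Reproducing 81.** The pooled risk is (0.30 + 2 × 0.06)/3 = 0.14. The pooled-variance formula for the control arm is

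n = [1.960 × √(0.14 × 0.86 × 1.5) + 0.842 × √(0.30 × 0.70 + 0.06 × 0.94/2)]² / 0.24² = (0.833 + 0.411)² / 0.0576 = 26.85.

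Rounded up, this is 27 controls and 54 on exenatide, 81 in all. The unrounded total is 80.6, so no attrition allowance is hidden in it.

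**Power formula for the scenarios.** Power = Φ{[(pC − pE) − 1.960 × S0]/S1}, where S0 is the standard error of the difference under the pooled risk and S1 the standard error under the two separate risks. At 27:54, (0.24 − 1.960 × 0.0818)/0.0939 = 0.85, which gives 80.2%. Exact enumeration of the chi-squared test gives 82.4%.

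**Patients without a 24-month result (assumed rates), counted out of the chi-squared comparison.**

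- 10% in both arms (24.3:48.6): (0.24 − 1.960 × 0.0862)/0.0990 = 0.72, power 76%. Exact at 24:49: 79%.
- 17% in both arms (22.4:44.8): (0.24 − 1.960 × 0.0898)/0.1031 = 0.62, power 73%. Exact at 22:45: 75%.
- 17% in the exenatide arm only (27:44.8): (0.24 − 1.960 × 0.0870)/0.0951 = 0.73, power 77%.

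**The same losses under the planned log-rank test.** Censored patients contribute follow-up until their last visit. Simulation at 27:54 and 30% versus 6% gave about 77-81% power for 10-17% loss in both arms. The result depends on when loss occurs and on whether diabetes is detected only at visits.

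**Stopping exenatide while remaining in follow-up.** This applies only if the 80% reduction describes patients who stay on treatment. Take 17% stoppers from the plan; the risk after stopping is an assumption.

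- Half the benefit kept (stoppers' risk midway, 18%): pE = 0.83 × 6% + 0.17 × 18% = 8.04%, z = 0.55, power 71%.
- No benefit kept (stoppers' risk 30%): pE = 0.83 × 6% + 0.17 × 30% = 10.08%, z = 0.28, power 61%.

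Exact enumeration gives 73% and 62%.

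**The case against.** Four objections have weight.

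**Loss is overcounted.** Deleting lost patients from a binary comparison ignores that the planned analysis is a log-rank test with censoring. This stands in part. The plan sized the trial on a chi-squared test, so its stated 80% should be examined on that basis, but the trial will be analysed in a way that recovers some of the loss. The exact chi-squared figure at 10% loss is also within a point of 80%.

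**Dilution may be counted twice.** If the cited reduction is an intention-to-treat estimate, it already includes stoppers, and the plan calls discontinuation similar outside transplantation. The 6% would then be the risk of the whole randomised arm, and the 61-71% figures would not apply. This stands as a condition, because the documents do not settle which kind of estimate it is.

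**The 17% is weak evidence.** It corresponds to about 3 of 17 recipients (exact 95% interval roughly 4-43%) treated for diabetes rather than prediabetes. It measures stopping the drug, not loss to follow-up, and says nothing about the control arm. Using 17% as a loss rate in both arms is therefore only an illustration. Visits, laboratory tests and biopsies follow standard care at all sites, which argues against heavy control-arm loss.

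**Stoppers need not be lost.** A reader might infer from the 30-day provisions that patients who stop exenatide have no 24-month assessment. The documents do not say so; the intention-to-treat statement and the two-year follow-up point the other way.

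None of this supplies an attrition allowance or makes 81 anything other than an evaluable number.

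**Conclusion.** The point holds in a limited form: 81 is the number assessed at 24 months that gives 80% power, and it is also the enrolment total. The stated power has no reserve for the withdrawal and loss that the section itself provides for.

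The attrition shortfall is probably a few percentage points. Its size rests on assumed loss rates, on the plan's 30% and 6% being right, and on how much partial follow-up the log-rank test recovers. The larger drop from stopping treatment rests on the further assumption that the 80% reduction is not an intention-to-treat effect, and 61% is its worst case.

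A reader might infer that the design has 61-76% power, or that 80% holds only if every patient keeps the full drug effect. The documents support neither. The 76% and 61% come from separate scenarios, one with loss and no dilution, the other with full dilution and no loss. They are not the bounds of a range: combining 10% loss with full dilution gives about 57%, outside it. If the 80% reduction is already an intention-to-treat effect, no dilution should be added at all.

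**What to change.** In the sample-size paragraph of the Statistical analysis plan:

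- State that 81 (54:27) is the number with a 24-month result that gives 80% power for 30% versus 6%.
- Name an assumed loss rate and give the power of 81 enrolled under it, saying whether the figure is for the chi-squared calculation or the log-rank analysis.
- State whether the 80% reduction is taken as an intention-to-treat effect. Include the 61-71% scenario only if it is not, and note that the 17% comes from 17 recipients treated for diabetes.
- Refer to these figures, scenario by scenario, when a negative result is interpreted. Do not merge them into one range.

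The cost is a few sentences and a somewhat less favourable power statement. No additional patients are needed, and no analysis or study procedure changes.

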- To compare the incidence of mesangial expansion >20% in patients treated with Exenatide SR + SOC vs. SOC alone at 24 months after kidney transplantation.
- To compare transplant kidney function in the two arms
- To compare the incidence of death by any cause in the two arms
- To compare the incidence of graft loss by any cause in the two arms.

Inclusion criteria:

- Recipients of solitary kidney transplants (i.e. not combined liver-kidney, pancreas-kidney etc.)
- Labs consistent with prediabetes, as determined at 4 and 12 months after transplantation: Prediabetes (fasting blood glucose 100-125 mg/dl; or 2 hr glucose 140-199 or HgbA1c 5.7-6.4%)

Exclusion criteria:

- Diabetes pre-transplantation
- Diabetes at 4 and 12 months
- <18 years of age
- eGFR <30 ml/min (estimated by MDRD equation from serum creatinine)
- Active acute cellular rejection including borderline (If treated and resolved, these patients can be included)
- BK nephropathy active
- History of pancreatitis, pre-existing moderate-to-severe gastroparesis, liver cirrhosis or family /personal history of multiple endocrine neoplasia 2 or medullary thyroid cancer
- Pregnant or breastfeeding women

Female Subject must be either:

- a. of non-child bearing potential
 - 1) Post-menopausal (defined as at least 1 year without any menses) prior to screening , or
 - 2) Documented surgically sterile or status post-hysterectomy
- b. Or if childbearing potential,
 - 1) Agree not to try and become pregnant during the study for at least 90 days after the final study drug administration.
 - 2) And have a negative serum or urine pregnancy test.
 - 3) And if heterosexually active, agree to consistently use two forms of highly effective birth control.

- Hypersensitivity to Exenatide

Criteria for Discontinuation of Medication:

- Decrease in renal function to eGFR to < 30 ml/min after study initiation
- Decrease in eGFR by 50% on the 2 consecutive measurements without otherwise identified cause which maybe correctable (like high immunosuppressive medication level, rejection, urinary tract infection, etc)
- Intolerable GI side effects despite the optimal therapy
- Thyroid tumor
- Pancreatitis
- Hypoglycemia

Study design/schedule

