The coordinating center will be the primary contact for this study and the data coordinating center: [name] and his program coordinator, M [REDACTED] L [REDACTED] ([REDACTED] and [contact])

1. The FDA investigator-initiated IND will be held by [name]
2. Contracts will preferentially be through the Coordinating Center with subcontracts to the other sites. Indirect costs will be charged only once (i.e. at the site where the funds are actually spent).
3. Protocols will be approved by local IRB (the three Mayo sites have a central IRB).
4. Data is entered into a common database with case-report forms similar to any FDA studies(MEDIDATA Rave case forms specific for transplant are already in place)
5. The Coordinating Center will be responsible for data cleanup, data reporting and reporting to the sponsors and the FDA.
6. Histology:
Mesangial expansion by light microscopy

Schedule of visits

Enrollment Day 122 (4 months)

	Enrollment Day 122 after KTx range 90-180 days	Day 7±3 Days Post enrollment	Monthly labs to 1 year per SOC	Day 90±7	Day 365 ±90 after KTx	Labs q3 months from 12-24 months	Day 730 ± 90 after KTx
Consent	x						
Labs	x	x	x		x	x	x
Clinic visit	x				x		x
Communication through phone call or EMR		x		x		x	
HgbA1c					x	x	x
Biopsy	x				x		x
Pregnancy test	x						

Enrollment Day 365 (1 year)

	Enrollment Day 365 after KTx range 300-420 days	Day 7±3 Days Post enrollment	Labs q 3 months per SOC	Day 90±7	Day 730 ± 90 after KTx
Consent	x				
Labs	x	x	x		x
Clinic visit	x				x
Communication through phone call or EMR		x		x	
HgbA1c					x
Biopsy	x				x
Pregnancy test	x				

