FUTURE DIRECTIONS: Given the pervasiveness of diabetes and prediabetes in kidney and other solid organ transplant recipients, well-designed clinical trials aimed at determining best therapy for preventing and improving treatment of diabetes after transplantation are desperately needed. The concomitant use of diabetogenic agents, including corticosteroids and calcineurin inhibitors, and the common weight gain experienced after transplant create a challenging environment to deal with these problems, but also emphasizes the importance of addressing these concerns. The completion of a prospective, feasibility trial will help obtain needed data about the safety, tolerability, and efficacy of GLP-1 receptor agonists in kidney transplant recipients and specifically Hispanic patients. Improved treatment of prediabetes and diabetes after kidney transplantation may portend the realization of goals to enhance long-term kidney graft outcomes, as well as improve the health and survival of these patients.

Specific Methods.

Prediabetes and diabetes are determined using standard serum blood glucose level determinations including: fasting serum glucose, 2 hour post serum glucose in an OGTT and HbA1c.

eGFR is based on serum creatinine levels using MDRD⁴⁸

Light Microscopy

Light microscopy will be used to determine the percentage of (1) global glomerulosclerosis (GGS) involving >20% of the glomeruli (GGS; 0 = 0%, 1 = ≤20%, 2 = >20%); and (2) mesangial matrix expansion (or mesangial sclerosis, MS) as defined as mild (1), moderate (2) and severe (3) averaged over all of the glomeruli in each biopsy sample

- 2. *2015 USRDS annual data report: Epidemiology of Kidney Disease in the United States*. Bethesda, MD: National Institutes of Health, National Institute of Diabetes and Digestive and Kidney Diseases;2015.

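### The secondary endpoint on mesangial expansion uses a 20% cut that the specified biopsy reading cannot produce

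*Combined protocol and SAP*

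**What the plan says.** The endpoint appears twice in the same words, under Study objectives (Secondary) and under Study endpoints (Secondary endpoints): "To compare the incidence of mesangial expansion >20% in patients treated with Exenatide SR + SOC vs. SOC alone at 24 months" after transplantation. It is a yes/no classification of each patient, compared between arms.

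How the lesion is read is described only in Specific Methods, Light Microscopy. The sentence opens "Light microscopy will be used to determine the percentage of" and then lists two items. Item (1) is global glomerulosclerosis, in three percentage classes ("GGS; 0 = 0%, 1 = ≤20%, 2 = >20" per cent). Item (2) is "mesangial matrix expansion (or mesangial sclerosis, MS) as defined as mild (1), moderate (2) and severe (3) averaged over all of the glomeruli".

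The histology line of the Data management plan adds only "Mesangial expansion by light microscopy". The Statistical analysis plan assigns the secondary endpoints to general linear mixed models and gives no rule for classifying a biopsy as above or below 20%. The Study design section describes the trial as open-label. No section describes reading biopsies without knowledge of the arm.

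**The concern.** The endpoint needs a percentage and a cut at 20%. The reading supplies an average of ordinal grades. The one 20% cut with a definition sits in the same sentence but belongs to a different lesion. Followed as written, the plan gives the analyst nothing from which to decide whether a patient has the endpoint.

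Someone would then have to supply a rule: any expansion at all, moderate or worse, or perhaps the glomerulosclerosis class above 20%. These rules would give different proportions, and the last answers a question about another lesion. In an open-label trial with no masked reading described, that choice could be made with allocation known. A reader of the results could not tell whether the rule was independent of the data.

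**Working it through.** **The plan's own figure.** The only sample-size figure concerns the primary endpoint: 30% control incidence, an 80% relative reduction (0.30 × 0.20 = 0.06), two-sided 5%, 80% power, 2:1 allocation. With k = 2 and pooled proportion (0.30 + 2 × 0.06)/3 = 0.14:

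- null term: 1.960 × √(1.5 × 0.14 × 0.86) = 0.833
- alternative term: 0.842 × √(0.30 × 0.70 + 0.06 × 0.94/2) = 0.411
- control n = (0.833 + 0.411)² / 0.24² ≈ 26.9, rounded up to 27; with 54 on exenatide the total is 81.

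The stated 81 reproduces. It uses no mesangial quantity, so nothing below affects it.

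**Endpoint and reading side by side.**

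| Needed for the endpoint | What the documents supply |
|---|---|
| A percentage for each biopsy | An average of grades 1 to 3 |
| What the 20% is a percentage of (mesangial area, or glomeruli) | Not stated |
| A link from grade or average to percentage | None |
| A value for a glomerulus with no expansion | Not stated |
| A 20% cut on this lesion | Defined only for global glomerulosclerosis |
| A classification rule in the analysis plan | None |

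**Could the average be converted?** There are two candidate meanings of the 20%.

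1. *Percentage of glomeruli affected.* Assume 10 glomeruli and a score of 0 for none.
   - Biopsy A has 2 glomeruli at grade 3 and 8 at 0. Its average is (2 × 3)/10 = 0.6, with 2/10 = 20% affected, so it is not above 20%.
   - Biopsy B has 3 glomeruli at grade 1 and 7 at 0. Its average is (3 × 1)/10 = 0.3, with 3/10 = 30% affected, so it is above 20%.
   - The biopsy with the lower average meets the endpoint and the one with the higher average does not. No threshold on the average can reproduce the endpoint.
2. *Percentage of mesangial area.* This would need area bands for mild, moderate and severe. None are given, so no conversion exists.

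**Does the choice of substitute matter?** The documents give no mesangial rates, so this is illustration only. Assume biopsy-level grades 0, 1, 2 and 3 in 60%, 25%, 10% and 5% of patients. A cut at grade 1 or above gives 25 + 10 + 5 = 40%, at 2 or above 10 + 5 = 15%, and at 3 it gives 5%. With 40%, 30%, 20% and 10% instead, the same cuts give 60%, 30% and 10%. The reported proportion would depend mainly on which rule was adopted.

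**The case against.** Several points on the other side deserve weight.

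- **The lead-in speaks of a percentage.** It grammatically covers both lesions, so a percentage may well be intended for mesangial expansion too. This is fair evidence of intent, and it makes recording a percentage the repair closest to the text. It does not rescue the text, because item (2) is then defined by grade.
- **Grades may be kept for each glomerulus.** A percentage of affected glomeruli could then be computed. The plan specifies only the average and never says that the 20% refers to glomeruli.
- **The biopsy data carry limited weight.** The Potential challenges section places the significance of biopsy changes over time outside what the trial sets out to settle, and describes these data as preliminary. This stands and limits the severity. It does not excuse a listed between-arm endpoint that cannot be derived.

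Three stronger readings are tempting, and the documents do not support them.

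- A reader might infer that the definition would be chosen after the arms are known. Nothing says so. The rule is unset, and it could still be fixed before any biopsy data are analysed by arm.
- A reader might attach a false-positive rate, for example 1 − 0.95³ = 14% for three candidate rules. That assumes independent tests, but cuts on one score are nested. It also assumes that all three would be tried and the best reported, which the plan does not suggest. With no mesangial rates in the documents, no figure is anchored to this trial.
- A reader might infer that a normal biopsy must score 1. The text does not say that; it states no score for none. Nor can this be combined with the 14%: if every biopsy scored at least 1, any mild grade or above would be true of everyone and could not yield a false positive.

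**Conclusion.** The concern holds in a limited form. The endpoint and the reading are two stated rules that do not meet, and the first cannot be derived from the second. This rests on comparing the sections, not on any assumed rate. The definition is open in an open-label trial with no masked reading described, so it could be settled with allocation known. That is a risk left open, not something the plan sets out to do.

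The effect is confined to one secondary endpoint. The primary endpoint, its analysis and the sample size are untouched. No numerical size can be given for the mesangial comparison. The proportions shown under the assumed grade distributions indicate only that the choice of rule matters. The change should be made, but it does not threaten the trial's main conclusion.

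**What to change.** Choose one of two routes and word it the same way in Study objectives, Secondary endpoints and Light Microscopy.

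1. **Preferred, because it keeps the endpoint.** Under Light Microscopy, have the reader record percent mesangial expansion for each biopsy, state what it is a percentage of, and use 0 for none. Keep the cut above 20%. Name a method for a binary outcome, since a general linear mixed model does not suit one.
2. **If only grades will be read.** Replace the 20% endpoint in both lists with a between-arm comparison of the averaged score at 24 months, and add a grade 0. This fits the mixed models already planned, but the score should stay on its own scale, because a logarithm cannot be taken of 0.

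Under either route:

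- Compare all randomised patients who have a 24-month biopsy, and report how many in each arm have none.
- Adjust for the enrolment biopsy, which both visit schedules already include. Excluding patients on its result would drop randomised patients and sit badly with the intention-to-treat statement.
- Date the rule before any biopsy data are analysed by arm.
- Label slides by study number without the arm.

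The cost is wording in three places, a sentence in the Statistical analysis plan, and one changed or added field where the reading is recorded. The biopsies are already standard of care and scheduled. The documents do not say who reads them at the three sites, so the effort of recording a percentage and masking the slides is for the sponsor to confirm. No extra patients or procedures are needed.
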